### **3.4 Risk and burdens**

Participants will not be asked to disclose or directly think about their experience of sexual assault. The materials developed is to provide psychoeducation and build self-compassion through a normalising framework that will ask participants to reflect on their sex lives and how past experiences can affect their experience of sex. This may be difficult and upsetting for some participants. In order to counter this risk, information and signposting regarding crisis psychological support will be provided to participants at the beginning and end of each self-

help resource throughout the intervention. Participants will have access to [name], Clinical Psychologist and two other clinicians at the Barts NHS Trust Sexual Wellbeing Service during the length of project for triage if adverse reactions are identified. Participants will be able to email the lead investigator and provide consent for the investigator inform [name] to get in touch with them. Participants will be informed they are able to reach the head investigator from 9am to 4pm on weekdays. Outside office hours they will be signposted to other support lines. It will be made clear to participants that besides this one appointment, the researchers cannot provide further advice or medical treatment

Participants should contact their GPs if they have concerns for their mental or physical health. Participants are required to provide GP details when providing informed consent. The GP will not be notified of the participants involvement in the study. We will only contact their GP if there are identified risk such as severe self-harming, suicidal risk or a significant deterioration in mental health. Under these circumstances, confidentiality may be breached. As the study is utilising a self-help intervention, there will be an expectation that participants will be able to make practical decisions about their readiness to begin the intervention, their ability to cope and access additional support if required. This expectation will be clearly outlined in the participant information sheet and consent form.

Participants will be assessed on their risk to self during screening and receive a follow-up screening call from the head investigator. Participants who disclose high risk who are not accessing mental health services will be excluded from participating to prevent further distress that may be triggered during the intervention. Participants will be made aware that the researcher cannot provide advice or medical treatment and that they should contact their GP as a first step if they have concerns regarding their mental or physical health. Participants will be

able to provide details of their GP who can be informed that they are taking part in the study, however this is not compulsory.

Overall, the potential benefits of this study are thought to outweigh the risk. The intervention content is based on compassion-focused therapy and content that is already used by Barts NHS trust Sexual Wellbeing Service to improve sexual wellbeing. Participants can access the materials while waiting to be seen by these services, both of which have a long wait time.

### **3.5 Study end definition**

The study will be considered finished when the statistical analysis has been conducted and completed as seen as appropriate.

### **3.6 Pause criteria**

If more than 4 participants within eight weeks get in contact with the chief investigator requesting a 1:1 support session provided by clinicians at Bart's NHS Foundation Trust Sexual Wellbeing Clinic due to adverse effects from the intervention, the study may be paused. This number was decided as it represents 25% of our recruitment goal. The study would have to be paused due to clinician availability. If this occurs, the researchers will have a meeting with the service lead at Bart's NHS foundation trust Sexual Well-Being Clinic. This meeting will discuss the feasibility of continuing the study and potentially pausing the study and changing the recruitment strategy.

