## **2.2 Recruitment and participant screening**

The study will be advertised through Barts NHS Trust Sexual Wellbeing Service with information put on leaflets circulated within the clinic. Clinicians may also provide an information sheet to clients with a weblink the study details and screening questionnaire.

Additional recruitment will be done on My Body Back, an organisation who works with women with experience of sexual assault, in London and Glasgow. My Body Back will advertise the study on its website and at its events, providing a web link to the study details and initial screening questionnaire. The intervention will be offered whilst women are on the waiting list. They will not lose their place on the waiting list if they take part.

General social media advertising will also be done through different charities and communities who work with female survivors of sexual assault. Potential participants will be encouraged to take some time to think about whether or not they would like to participate. Individuals will be

informed that participation is on a voluntary basis and consent can be withdrawn at any time. They will also not lose their place on the waiting list for services. Statistical power analyses have been underdeveloped for SCED (Arntz et al., 2013). For a SCED, only 1 participant is required for analysis but, Lanovaz & Rapp (2015) suggest a '3 point guideline' as the minimum requirement for control of study design. Having more than 3 participants will also improve the generalization of findings (Kratochwill et al., 2013). Considering this and to account for attrition, we aim to recruit 20 participants with a minimum sample size of 6 participants.

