#### *2.2.3 Criteria for premature withdrawal*

Participants will be able to withdraw from the study at any point by informing the chief investigator

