## **4. Assessment of safety**

As the study is utilising a self-help intervention, there will be an expectation that participants will be able to make practical decisions about their readiness to begin the intervention, their ability to cope and access additional support if required. This expectation will be clearly outlined in the participant information sheet and consent form. Participants will be able to email the lead investigator and provide consent for the investigator inform Clinicians at Bart's NHS Foundation trust to get in touch with them. Participants will be informed they are able to reach the head investigator from 9am to 4pm on weekdays. Outside office hours they will be signposted to other support lines.

If participants report identified risks, they will be supported through the 1:1 personal support session provided by Bart's NHS Foundation Trust, Sexual Wellbeing Service. However, confidentiality may be breached if the clinicians or the chief investigator are still concerned about risk. The chief investigator will first discuss this with the participant if this occurs. Subsequently, an urgent email (GP Letter V2) will be sent to the participant's GP via NHS email. A phone call will also be made to the GP to ensure the GP is informed.

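### The only pause rule counts requests to the investigator for a Barts 1:1 session, so harms taken to a GP or support line, or ending in withdrawal, need not reach the count

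*Combined protocol and SAP*

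**What the plan says.** All references are to the combined protocol and SAP.

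- **What is counted.** Section 3.6 opens "If more than 4 participants within eight weeks" and counts those who "get in contact with the chief investigator requesting a 1:1 support session provided by clinicians" at the Barts clinic because the intervention has affected them badly. The number is explained as follows: "This number was decided as it represents 25% of our recruitment goal". Section 2.2 gives the goal: "we aim to recruit 20 participants with a minimum sample size of 6 participants".
- **What follows.** One sentence of section 3.6 makes a pause discretionary. Another says "The study would have to be paused due to clinician availability". The section then provides for a meeting with the service lead.
- **Where participants are sent.** Section 3.4 says twice that they should go to their GP with health concerns. The second time it says that "they should contact their GP as a first step if they have concerns regarding their mental or physical health". Section 4, like section 3.4, adds: "Outside office hours they will be signposted to other support lines". Both sections also let a participant email the investigator, who can then ask Barts clinicians to contact her.
- **What comes back.** Section 2.2 states that the investigator learns of increased risk only through the participant's own email. Sections 2.2 and 3.4 say the GP is not told of participation, but a later paragraph of 3.4 says the GP can be told, optionally.
- **Withdrawal.** Section 2.2.3 reads in full: "Participants will be able to withdraw from the study at any point by informing the chief investigator".

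**The concern.** A pause rule can act only on what it counts. Here a woman is counted if three things hold: she contacts the investigator, she asks for the Barts session, and the reason is an adverse effect. The plan gives her other legitimate things to do when distressed, and describes no path from those back to the count. It describes no adverse event form, scheduled safety question or score-based check that would fill the gap.

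The rule could therefore stay silent while harm builds up and weekly sessions go on being released. That matters in this study: the plan expects that the material may upset some participants, professional contact is minimal, and women with fleeting suicidal thoughts may be enrolled if they have strong protective factors (section 2.2.2). Feasibility and acceptability are the primary objective, and withdrawal or help-seeking caused by distress is direct evidence on both.

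**Working it through.** **1. The plan's own figure.** More than 4 means a first trigger at 5. With a goal of 20, 5/20 = 25%, which reproduces the stated basis. (Taking the number as 4 would give 4/20 = 20%, or imply a goal of 4/0.25 = 16.) The threshold is not in dispute. At the minimum sample of 6, the trigger needs 5/6 = 83% of participants.

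**2. Channels set against the count.**

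| What the participant does | Where described | Reaches the 3.6 count? |
|---|---|---|
| Emails the investigator and asks for the Barts session because of adverse effects | 3.4, 3.6, 4 | Yes |
| Reports a risk and is given the session under section 4 | 4 | Unclear: 3.6 counts requesting, section 4 speaks of reporting |
| Goes to her GP | 3.4 | Not unless she also emails; no report back described |
| Uses a support line out of hours | 3.4, 4 | Not unless she also emails |
| Withdraws | 2.2.3 | Not unless she also asks for the session; no reason or link described |

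The investigator can be reached from 9am to 4pm on weekdays: 5 × 7 = 35 of 168 hours, or 21% of the week. An email can still be sent later, so this limits prompt contact and does not close the route.

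**3. Illustration of size.** The documents give neither the harm rate p nor the share c of harmed participants who make a counted request. Both are assumptions. With n = 20 and independent participants, the number counted is binomial with probability q = p × c, and

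P(trigger) = 1 − Σ(k = 0 to 4) C(20,k) q^k (1 − q)^(20−k).

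- p = 25%, c = 100%: q = 0.25. The terms for k = 0 to 4 are 0.0032, 0.0211, 0.0669, 0.1339 and 0.1897, with sum 0.4148, so P = 0.585.
- p = 25%, c = 50%: q = 0.125. The terms are 0.0692, 0.1977, 0.2684, 0.2300 and 0.1397, with sum 0.9050, so P = 0.095.

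| Assumed harm rate | c = 100% | c = 50% | c = 25% |
|---|---|---|---|
| 25% | 58.5% | 9.5% | 0.7% |
| 40% | 94.9% | 37.0% | 4.3% |
| 50% | 99.4% | 58.5% | 9.5% |

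The eight-week window is ignored, so these are upper bounds.

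**4. The same in counts.** To expect 5 counted requests, 5/c participants must be harmed: 5/0.5 = 10 at half capture, and 5/0.25 = 20, the whole goal, at quarter capture. If exactly 5 of 20 are harmed and c = 50%, all five must ask: 0.5^5 = 3.1%.

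**The case against.** The strongest reply is that the instruction most specific to adverse reactions is the counted one. Section 3.4 offers Barts triage for exactly that purpose, reached by emailing the investigator, and section 4 repeats the email route. The GP instruction concerns mental and physical health in general. Under section 4 a GP escalation normally follows a 1:1 session, so it overlaps the count. Using a support line does not prevent a later email, a withdrawing participant contacts the investigator anyway, and the feedback form at follow-up lets completers describe harm. How wide a trigger should be in a self-help study of 6 to 20 women is partly a matter of judgement.

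Much of this stands, and it rules out several stronger readings that a reader might infer:

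- That harms handled as instructed can never be counted. The email route can feed the count.
- That only one of five routes is counted. The routes overlap and are not equally likely, so a tally of them measures nothing.
- That the rule tracks clinic capacity and not harm. Capacity is the reason given for pausing, but the counted event is tied to adverse effects.
- That a published count would understate harm. Nothing says the pause count will be reported.
- That GPs are certainly unaware of the study. The statements conflict.
- That no reason is ever asked at withdrawal. The protocol describes none, but the information sheet and consent form are not among the documents reviewed.

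The reply does not supply a path from GP, support line or withdrawal to the count. It relies on the participant choosing to make a further, separate request.

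**Conclusion.** The gap is real but limited. As written, harm that stays with a GP or support line, or ends in withdrawal, need not enter the only pause count, and the plan describes nothing else that would bring it to the investigator's notice during delivery. This conclusion rests on the text alone.

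Its size cannot be read from the documents. At an assumed 25% harm rate in 20 participants, halving capture lowers the chance of triggering from about 58% to about 10%. The direction is certain for any capture below 100%. The amount depends on assumed harm rates and shares, on independence, and on ignoring the window.

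Three sets of statements also conflict: the discretionary and the obligatory wording of the consequence within section 3.6; the GP-first instruction in section 3.4 and the email route in sections 3.4 and 4; and the GP-notification statements in sections 2.2 and 3.4, including within 3.4 itself.

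**What to change.** Keep the number and the eight-week window in section 3.6. Let the count that prompts the already planned meeting with the service lead include, besides session requests:

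- risk reports or GP escalations under section 4;
- withdrawals where the participant volunteers distress as the reason;
- help sought elsewhere because of the materials, as reported in the survey item below.

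Count each woman once. The first two already reach the investigator. For the third, add one optional tick item to the daily Qualtrics survey of phases A and B, and add an optional reason box at withdrawal.

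The sponsor should also reconcile the three sets of conflicting statements named in the verdict. Which consequence, first contact or notification rule is right is for the sponsor and clinicians to decide.

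The cost is a rewording of section 3.6, two optional survey fields, and the investigator's time to look at the daily item while data are being collected. The meeting may be prompted somewhat earlier, sometimes by events that used no Barts clinician, which the meeting can weigh. Daily surveys end with phase B, so help sought in the following month would still be missed unless the participant makes contact.

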## **4. Assessment of safety**

As the study is utilising a self-help intervention, there will be an expectation that participants will be able to make practical decisions about their readiness to begin the intervention, their ability to cope and access additional support if required. This expectation will be clearly outlined in the participant information sheet and consent form. Participants will be able to email the lead investigator and provide consent for the investigator inform Clinicians at Bart's NHS Foundation trust to get in touch with them. Participants will be informed they are able to reach the head investigator from 9am to 4pm on weekdays. Outside office hours they will be signposted to other support lines.

If participants report identified risks, they will be supported through the 1:1 personal support session provided by Bart's NHS Foundation Trust, Sexual Wellbeing Service. However, confidentiality may be breached if the clinicians or the chief investigator are still concerned about risk. The chief investigator will first discuss this with the participant if this occurs. Subsequently, an urgent email (GP Letter V2) will be sent to the participant's GP via NHS email. A phone call will also be made to the GP to ensure the GP is informed.

## 5. Data security, management and confidentiality

### **5.1 Data storage, handling and confidentiality**

All computerised data will be stored and encrypted on a password protected USB drive that adheres to the NHS confidentiality standards.

Participants will provide email address so that they can be sent links to the self-help materials each week as well as links to questionnaire and prompt emails. Names are only used when giving consent and for demographic information. Participants will then be allocated a participation ID number for reference to fill in questionnaires and not linked to names. A separate key associating the ID number with the participants' names will be stored apart from

the data and destroyed once it is no longer necessary to contact participants or obtain further information about them (e.g., once a journal article is published), this file will be password protected.

All information will be submitted through Qualtrics which is a secure and confidential platform. Data will be downloaded, password protected and kept on a secure USB stick, only accessible to the researcher.

Database containing any personal information will be deleted following the final write-up of the research.

No members of the research team will have access to participants' personal medical records or any clinical data beyond that voluntarily provided by the participants when they choose to participate in the study. This information provided will only be seen by the chief investigator and will be kept securely in a password protected database, separately to the research data.

Data will be analysed on a personal laptop by the Chief Investigator at Royal Holloway, University of London. All data will be saved on a password protected encrypted USB (approved by RHUL and sponsor) that only the chief investigator has access to. This will not include any personally identifiable data. Data is anonymised and each participant is given a 4-digit participant code using random numbers and letters.

## **5.2 Data preservation**

The research data will be kept in a database (as discussed in A36) which will be retained by [name], who is supervising this research on behalf of Royal Holloway, University of London. Data is kept for up to five years, for audit purposes.

This database will contain no personally identifiable information and will be password protected. Only [name] will hold the password. Consent forms will be kept for 2 years.

## 6. Publication of results

The study will be published as a doctoral thesis and may be published in peer reviewed scientific journals or presented in conferences.

